#### **12.4.4 Sensitivity and Supportive analyses**

##### **Sensitivity analyses**

To assess the robustness of the primary analysis results, several sensitivity analyses will be explored. The details will be described in the statistical analysis plan.

##### **Supportive analyses**

A supportive analysis will involve estimation of treatment effects and contrasts (anti-inflammatory agent vs. placebo) within subgroups (e.g., MCI or mild AD). The details will be described in the statistical analysis plan.

## 12.5 Analysis of secondary endpoints

### 12.5.1 Efficacy and/or Pharmacodynamic endpoint(s)

#### Memory, cognition, executive function, and neuropsychiatric outcomes

The "memory function" composite score is obtained by averaging the following z-scores from the NTB: RAVLT immediate and delayed scores.

The "executive function" composite score is obtained by averaging the following three z-scores from the NTB: Wechsler Memory Scale Digit Span, COWAT, and CFT.

The DSST is an attention-demanding component of the Wechsler Adult Intelligence Scale-IV. The DSST score is the number of digits coded correctly in a fixed amount of time, whereby higher scores denote better performance.

Commercially Confidential Information

The Everyday Cognition (ECog) scale is a validated informant-based measure comprised of 39 items covering six cognitively relevant domains ([Farias et al 2008](#)). Each item is scored on a 4-point scale (1=better or no change compared to 10 years earlier, 2=questionable/occasionally worse, 3=consistently a little worse, 4=consistently much worse). An "I don't know" response is also included. The total ECog score is calculated as the sum of all 39 items, and the average score is derived from the mean average of all responses. If the response is "I don't know", then the item is not included in the calculation. The lower total ECog and average ECog scores indicate better performance.

The NPI-D and the eNeuropsychiatric At-Home assessment are study partner reported outcome measures of 12 neuropsychiatric symptoms and the distress associated with these disturbances. The NPI-D total score is in the range from 0 to 144, with higher values indicating greater disturbance. The eNeuropsychiatric at-home assessment contains a subset of questions from the NPI-D and is scored similarly.

The memory function composite score, the executive function composite score, the DSST score, the overall eCognitive test scores, the total ECog score **PET CCI**, and the total NPI-D score will be analyzed using the same methodology as for the primary endpoint ([Section 12.4](#)).

#### PET CCI

The PET CCI will be examined at baseline and upon completion of week 12. An analysis of covariance (ANCOVA) will be performed on the log-transformed ratio to baseline of the relevant PET CCI outcome measure (details of the derivation of the outcome will be delineated in the statistical analysis plan). The model will include treatment group as a classification factor, log-transformed PET CCI, as well as other important baseline prognostic factors such as age and MMSE score, as covariates. The least squares estimates of mean treatment effects and treatment contrast, with corresponding 90% confidence intervals will be back transformed to the original scale. This analysis will be performed for each cohort separately. If deemed appropriate, data from the placebo group across different cohorts may be pooled.

**Total CCI**

For biotherapeutic agents, measurement of total CCI concentrations CCI is used as a PD marker to evaluate CCI. Total CCI concentration data will be listed by treatment, participant, and visit/sampling time point. Agent-specific information is detailed in [Section 17](#), as applicable.

**12.5.2 Safety endpoints**

For all safety analyses, the safety set will be used.

**Adverse events**

All information obtained on adverse events will be displayed by treatment group and participant.

The number (and percentage) of participants with treatment emergent adverse events (events started after the first dose of study medication or events present prior to start of double-blind treatment but increased in severity based on preferred term) will be summarized in the following ways:

- by treatment, primary system organ class and preferred term.
- by treatment, primary system organ class, preferred term and maximum severity.

Separate summaries will be provided for study medication related adverse events, death, serious adverse events, other significant adverse events leading to discontinuation.

The number (and proportion) of participants with adverse events of interest will be summarized by treatment.

A participant with multiple adverse events within a primary system organ class is only counted once towards the total of the primary system organ class.

**Vital signs**

All vital signs data will be listed by treatment group, participant, and visit/time and if ranges are available, abnormalities (and relevant orthostatic changes) will be flagged. Summary statistics will be provided by treatment and visit/time.

**Standard 12-lead ECG**

All ECG data will be listed by treatment group, participant and visit/time; abnormalities will be flagged. Summary statistics will be provided by treatment and visit/time.

**Clinical laboratory evaluations**

All laboratory data will be listed by treatment group, participant, and visit/time and if normal ranges are available abnormalities will be flagged. Summary statistics will be provided by treatment group and visit/time.

**Other safety evaluations**

C-SSRS data will be listed by treatment, participant, and visit/time; abnormalities will be flagged. Summary statistics will be provided by treatment and visit/time, if deemed relevant.

## Immunogenicity

For biotherapeutic agents, all immunogenicity results will be listed by treatment group, participant, and visit/time. Agent-specific information is detailed in [Section 17](#), as applicable.

### 12.5.3 Pharmacokinetics

Agent serum concentration data (i.e. for biotherapeutic agents) or plasma concentration data (i.e. for low molecular weight agents) will be listed by treatment, participant, and visit/sampling time point.

Commercially Confidential Information

Summary statistics will include mean (arithmetic and geometric), SD, CV (arithmetic and geometric), median, minimum, and maximum.

Commercially Confidential Information

Pharmacokinetic parameters will be listed by treatment and participant. Descriptive summary statistics will include mean (arithmetic and geometric), SD, and CV (arithmetic and geometric), median, minimum, and maximum. An exception to this is  $T_{max}$  where median, minimum, and maximum will be presented, as applicable.

CSF to serum ratio will be calculated by the ratio of agent exposure in CSF to that in serum (for biotherapeutic agents) or plasma (for low molecular weight compounds).

Additional agent-specific information and pharmacokinetic parameters are detailed in [Section 17](#).

### 12.5.4 PK/PD relationships

The relationships between individual PK profiles or derived PK parameters and efficacy/PD measurements may be explored using graphical approaches (e.g., scatter plots) and regression analysis as appropriate. Agent-specific information is detailed in [Section 17](#), as applicable.

Commercially Confidential Information

Commercially Confidential Information

Comercially Confidential Information

## 12.8 Sample size calculation

### 12.8.1 Primary endpoint(s)

For the primary endpoint, change in NTB total z-score at week 24, data from 36 evaluable participants per arm (investigational agent and placebo) provides ~80% power to detect a statistically significant difference between the two groups at a 1-sided  $\alpha=0.10$  when the true standardized mean difference is 0.5. The effect size of 0.5 corresponds a moderate treatment effect which is thought to represent a clinically meaningful improvement at 24 weeks. To account for 15% dropout rate, approximately n=86 participants randomized in a 1:1 ratio would be needed to address the primary objective. These calculations take into account results of the published study by Frölich et al. (2019), where the standard deviation of the change in NTB total z-score was estimated to be ~0.38 for both active and placebo groups.

For smaller true effect sizes, the power is lower ([Table 12-1](#) below).

**Table 12-1 Sensitivity of power to changes in assumptions**

SD (common to 2 arms)	True mean difference ( $\Delta$ )	True effect size ( $\Delta/SD$ )	alpha (1-sided)	Power
0.38	0.19	0.5	10%	80%
0.38	0.152	0.4	10%	66%
0.38	0.114	0.3	10%	50%
0.38	0.095	0.25	10%	41%

It is assumed that n=86 participants are randomized in a 1:1 ratio and the dropout rate is 15% (thus we have 72 evaluable participants, 36 per arm)

### 12.8.2 Secondary endpoint(s)

For the secondary endpoint, PET CCI, a comparison between an investigational agent and placebo will be based on data from approximately 10 participants per arm. Assuming inter-participant variability of 20%-25%, the power to detect statistically significant treatment difference (using 1-sided  $\alpha=0.05$ ) is shown in [Table 12-2](#) below. For the 25% true mean reduction in microglial activation due to an anti-inflammatory agent vs. placebo, there is at least 87% power (assuming coefficient of variation is 25% or less).

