### 3 Study design

This is a randomized, placebo-controlled, participant- and investigator-blinded platform study in participants with MCI due to AD or mild AD who have evidence of peripheral inflammation.

The EXPLAIN-AD study uses a platform type design to investigate “multiple targeted therapies in the context of a single disease in a perpetual manner” ([Woodcock and LaVange 2017](#)).

Commercially Confidential Information

For each completed cohort, the data analysis will be performed upon final database lock for the cohort, and the results will be reported upon completion of each cohort in an end of cohort report.

Each cohort in the study will undergo the same study evaluations and assessments. Each cohort will include a screening period (Day -60 to Day -8), followed by a baseline period of 7 days (Day -7 to Day -1), a treatment period of 20 weeks (Day 1 to Day 141), and a study completion evaluation [End of Cohort (EOC1)] approximately 30 days after the last agent administration (Day 171). For agents with longer half-lives, such as monoclonal antibodies, the same study design will be followed; however, an additional post-treatment follow-up visit (EOC2) will occur on Day 281.

Participants who meet the eligibility criteria at screening will have baseline assessments performed. All baseline safety evaluation results must be available prior to randomization. All participants will undergo assessments of cognition, neuropsychiatric symptoms and function (activities of daily living) at various time points throughout the duration of the trial.

[figure not shown]
Moreover, all participants will undergo CSF sampling at screening and following completion of 12 weeks treatment. In addition, blood samples will be collected throughout the study (see [Table 8-1](#) assessment schedule and [Section 17](#) agent-specific sample collection table).

In addition, a sub-set of these same participants (up to 22 per investigational agent/matching placebo) will undergo PET CCI imaging at baseline and following completion of the first 12 weeks treatment. Alterations in activated microglia and astrocytes due to therapeutic intervention will be measured using a PET CCI radioligand, CCI . PET imaging in

this subset of participants and analysis of CSF and/or serum samples in all participants will provide measures of both central and peripheral inflammation following treatment with an investigational agent/matching placebo.      Commercially Confidential Information

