**Table 12-2 Power for treatment comparison using log-transformed PET CCI at week 12**

Coefficient of variation (CV)	True mean reduction (active vs. placebo)	$\alpha$ (1-sided)	Power
0.2	30%	5%	99%
0.2	25%	5%	93%
0.2	20%	5%	78%
0.25	30%	5%	93%
0.25	25%	5%	81%
0.25	20%	5%	62%

The assumed sample size is n=20 (10 per arm)

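### The text promises at least 87% power for the PET comparison when the CV is 25% or less, but 10 per arm gives 81%, as the plan's own table shows

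*Protocol*

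**What the plan says.** Protocol 12.8.2 states that the PET comparison of agent with placebo "will be based on data from approximately 10 participants per arm", tested at one-sided alpha 0.05, with between-participant variability assumed to lie between 20% and 25%. The paragraph closes with a summary for one scenario, a true reduction of 25% on the agent relative to control. Its claim is: "there is at least 87% power (assuming coefficient of variation is 25% or less").

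The paragraph refers to Table 12-2, titled "Power for treatment comparison using log-transformed PET CCI at week 12", whose footnote reads "The assumed sample size is n=20 (10 per arm"). For the 25% reduction the table gives 93% power at a CV of 0.20 and 81% at a CV of 0.25.

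SAP 3.2 and SAP Table 3-2 repeat both the sentence and the table with the same figures. Protocol section 3 caps the imaging subset: "a sub-set of these same participants (up to 22 per investigational agent/matching placebo) will undergo PET".

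**The concern.** The sentence gives a lower bound on power over a range of CVs. Power falls as the CV rises, so that bound has to be the power at the top of the range, a CV of 25%. The table beside it prints 81% for exactly that case. The text and the table use the same effect, alpha and sample size, so they cannot both be right.

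The number matters because of how PET is used. Protocol 4.3 treats a positive PET result as proof of mechanism for an agent, and cites 12.8.2 to support the view that PET needs fewer participants than the other endpoints. Participants in the subset also undergo arterial cannulation and radiation exposure (Protocol 4.9). A reader who relies on the sentence would think a true 25% reduction is missed 13% of the time at worst. By the table it is missed 19% of the time.

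**Working it through.** **Inputs** (Protocol 12.8.2 and Table 12-2; the same in SAP 3.2 and Table 3-2)

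- n = 10 per arm, so 18 degrees of freedom
- one-sided alpha = 0.05, so the critical value is t(0.95; 18) = 1.734
- true reduction r = 25%, ratio 0.75
- CV = 0.20 or 0.25
- analysis on the log scale

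**Method.** Two-sample t-test on log values:

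- difference: delta = -ln(1 - r)
- SD = sqrt(ln(1 + CV²))
- noncentrality = delta / (SD × sqrt(2/n))
- power = probability that a noncentral t with 2n - 2 df exceeds the critical value

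**Step 1: reproduce the plan's table**

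| CV | Reduction | delta | SD | Noncentrality | Power, recomputed | Power, stated |
|---|---|---|---|---|---|---|
| 0.20 | 30% | 0.3567 | 0.1980 | 4.03 | 98.7% | 99% |
| 0.20 | 25% | 0.2877 | 0.1980 | 3.25 | 93.0% | 93% |
| 0.20 | 20% | 0.2231 | 0.1980 | 2.52 | 78.2% | 78% |
| 0.25 | 30% | 0.3567 | 0.2462 | 3.24 | 92.9% | 93% |
| 0.25 | 25% | 0.2877 | 0.2462 | 2.61 | 80.7% | 81% |
| 0.25 | 20% | 0.2231 | 0.2462 | 2.03 | 62.0% | 62% |

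All six entries agree after rounding, so this is evidently the method behind the table.

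**Step 2: the case in the sentence.** At r = 25% and CV = 0.25, the standard error is 0.2462 × sqrt(2/10) = 0.1101 and the noncentrality is 0.2877 / 0.1101 = 2.61. Power is 80.7%, which rounds to the table's 81%.

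**Step 3: does another convention give 87% at 10 per arm?** For CV 0.25 and a 25% reduction:

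| Variant | t-test | Normal approximation |
|---|---|---|
| As stated (log scale, one-sided 0.05) | 80.7% | 83.3% |
| Log-scale SD set equal to the CV | 79.7% | 82.3% |
| Two-sided 0.05 | 69.6% | 74.3% |
| One-sided 0.10 | 89.8% | 90.8% |
| Untransformed difference, one-sided 0.05 | 69.4% | 72.3% |

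None gives 87%. The only variants above it use an alpha that the plan does not use for this endpoint.

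**Step 4: what would be needed for 87%?**

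- *More participants*, CV 0.25: 11 per arm gives 84.2% and 12 per arm gives 87.0%. If the cap of 22 is read as a total split 1:1, it allows 11 per arm.
- *Less variability*, 10 per arm: power is 87.25% at CV 0.225 and 86.0% at CV 0.23. It equals 87% at a CV of about 0.226. The part of the assumed 20% to 25% range above 22.6%, nearly half of it, does not support the sentence.

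**Size of the error.** 87 - 81 = 6 percentage points of power. The miss probability is 100 - 81 = 19% instead of 100 - 87 = 13%, a ratio of 19/13 ≈ 1.5.

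**The case against.** The strongest objection is that nothing now depends on the sentence. SAP 1.1 records that the study stopped after 34 participants were randomized, SAP 2.6.3 says PET data will only be listed because one participant has data, and SAP section 4 cancels the PET interim analysis. The correct 81% is also printed directly below the sentence, the endpoint is secondary, and the primary sample size of 86 is unaffected. All of this is true and limits the practical effect. It does not make the sentence correct. Protocol 12.8.2 is also part of the core text, which Protocol 4.1 does not expect to change significantly as cohorts are added, so the wrong figure would carry over to any later cohort. The documents describe no such cohort yet.

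Two further cautions stand.

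- The origin of 87% is not known. It matches 12 per arm (24 in total), and SAP section 4 mentions 24 patients completing PET. But it is also the simple average of 93% and 81%, and close to the power at the midpoint CV of 22.5% (87.25%). The finding does not need an explanation of where the figure came from.
- The protocol does not say how the 22 participants split between arms, so 11 per arm is an assumption.

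**Conclusion.** The concern holds. For a 25% true reduction, a CV of 25% or less, 10 per arm and one-sided alpha 0.05, the minimum power is 81% (80.7% before rounding), not 87%. The tables are right and the summary sentence is wrong in both documents. Under the assumed 1:1 split, the full subset of 22 would still give only 84%.

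The 81% rests on the model that reproduces the table: log-normal data, equal variances, an unadjusted two-sample t-test, and the stated CV taken as the variability of the analysed quantity. The contradiction between sentence and table needs none of these assumptions. The error changes no Cohort 1 analysis and does not touch the primary sample size. It is a misstated operating characteristic for the proof-of-mechanism readout and should be corrected.

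**What to change.** In Protocol 12.8.2 and SAP 3.2, change the stated minimum power from 87% to 81% for a 25% reduction, CV of 25% or less and 10 per arm. Giving the range, 81% at a CV of 25% to 93% at a CV of 20%, would be clearer still. The tables need no change. SAP 3.2 needs no added note that the comparison has been dropped, because SAP 2.6.3 already says the PET data will only be listed.

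If 87% at a CV of 25% was the intended target, the planned number per arm and the cap on the subset would have to be revisited for later cohorts: by this calculation it takes 12 evaluable participants per arm, or 24 in total, against a cap of 22.

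The cost is one number in each document, with no reanalysis. The stated power becomes less favourable.

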**Table 12-2 Power for treatment comparison using log-transformed PET CCI at week 12**

Coefficient of variation (CV)	True mean reduction (active vs. placebo)	$\alpha$ (1-sided)	Power
0.2	30%	5%	99%
0.2	25%	5%	93%
0.2	20%	5%	78%
0.25	30%	5%	93%
0.25	25%	5%	81%
0.25	20%	5%	62%

The assumed sample size is n=20 (10 per arm)

## 13 Ethical considerations and administrative procedures

### 13.1 Regulatory and ethical compliance

This clinical study was designed and shall be implemented, executed and reported in accordance with the International Conference on Harmonisation (ICH) Harmonized Tripartite Guidelines for Good Clinical Practice, with applicable local regulations (including European Directive 2001/20/EC, US CFR 21), and with the ethical principles laid down in the Declaration of Helsinki.

### 13.2 Responsibilities of the investigator and IRB/IEC

Before initiating a trial, the investigator/institution must obtain approval/favorable opinion from the Institutional Review Board/Independent Ethics Committee (IRB/IEC) for the trial protocol, written informed consent form, consent form updates, participant recruitment procedures (e.g. advertisements) and any other written information to be provided to participants. Prior to study start, the investigator is required to sign a protocol signature page confirming his/her agreement to conduct the study in accordance with these documents and all of the instructions and procedures found in this protocol and to give access to all relevant data and records to Novartis monitors, auditors, Novartis Quality Assurance representatives, designated agents of Novartis, IRBs/IECs, and regulatory authorities as required. If an inspection of the clinical site is requested by a regulatory authority, the investigator must inform Novartis immediately that this request has been made.

### **13.3 Publication of study protocol and results**

The protocol will be registered in a publicly accessible database such as clinicaltrials.gov and as required in EudraCT. In addition, after study completion (defined as last patient last visit) and finalization of the study report the results of this trial will be submitted for publication and posted in a publicly accessible database of clinical trial results, such as the Novartis clinical trial results website and all required Health Authority websites (e.g., Clinicaltrials.gov, EudraCT etc.).

For details on the Novartis publication policy including authorship criteria, please refer to the Novartis publication policy training materials that were provided to you at the trial investigator meetings.

### **13.4 Quality Control and Quality Assurance**

Novartis maintains a robust Quality Management System (QMS) that includes all activities involved in quality assurance and quality control, to ensure compliance with written Standard Operating Procedures as well as applicable global/local GCP regulations and ICH Guidelines.

Audits of investigator sites, vendors, and Novartis systems are performed by auditors, independent from those involved in conducting, monitoring or performing quality control of the clinical trial. The clinical audit process uses a knowledge/risk based approach.

Audits are conducted to assess GCP compliance with global and local regulatory requirements, protocols and internal SOPs, and are performed according to written Novartis processes

## **14 Protocol adherence**

This protocol defines the study objectives, the study procedures and the data to be collected on study participants. Additional assessments required to ensure safety of participants should be administered as deemed necessary on a case by case basis. Under no circumstances including incidental collection is an investigator allowed to collect additional data or conduct any additional procedures for any purpose involving any investigational drugs under the protocol, other than the purpose of the study. If despite this interdiction prohibition, data, information, observation would be incidentally collected, the investigator shall immediately disclose it to Novartis and not use it for any purpose other than the study, except for the appropriate monitoring on study participants.

Investigators ascertain they will apply due diligence to avoid protocol deviations. If an investigator feels a protocol deviation would improve the conduct of the study this must be considered a protocol amendment, and unless such an amendment is agreed upon by Novartis and approved by the IRB/IEC and Health Authorities, where required, it cannot be implemented.

